Participants will be selected two to three weeks prior to the starting date of the program. Selection will be based using administrative data from Genesis Foundation. We will use this information to randomly assign a total of 640 mothers or primary care givers into the program and 640 into a control group. Participants will be assigned to a 16-member group intervention group in the ECDC closest to their residence. Groups will meet once per week for approximately 3 hours per session.

Subjects assigned to the control group, and those in centers assigned to the intervention but not randomly selected to participate in the program, will continue benefiting from the services available to all families affiliated with child development centers in the municipality of the intervention.

Due to local operation and implementation restrictions, the program will be delivered in four sequential cohorts of approximately 160 participants in the intervention arm and 160 participants in the control arm per cohort. The total number of intervention groups will vary per cohort starting with 9 groups in each of the two cohorts of 2018 and increasing to 12 groups for each of the two cohorts in 2019. After the implementation of these four sequential cohorts, we will reach 640 participants in the intervention arm, and 640 subjects in the control arm.

The implementation of the program will be led by a team of six social workers who participated in a three-week intensive training. The team of trained social workers will be assigned into three dyads. Each dyad will lead the implementation of the program among 3 to 4 groups per cohort and complete implementation and debriefing logs on the progress of the session and the participants. The implementation team, in addition, will be supervised by three expert coaches on a weekly basis. The supervision scheme aims to guarantee the quality and fidelity of the intervention but also to provide reflexive support to mitigate burn-out and symptoms of vicarious trauma.

To ensure adherence, we will implement the following actions: First, sessions will be held during a day and time convened with the participants. Second, community health workers will make weekly phone calls to follow-up on each participant's needs and progress and encourage attendance. We followed this strategy during the implementation pilot and observed that 94% of the mothers who participated in the program completed all the sessions.

- **Outcomes (End Points)**

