Eligible subjects will also be informed that their decision to participate or not in *Semillas de Apego* and the data collection does not have any consequence on access to Genesis Foundation's programs in the municipality, including their children's access to the ECDC, or their participation in standard community groups and activities. Once eligible subjects accept to participate, they will be contacted by the data collection firm, which will coordinate the date and time of the baseline data collection.

We will follow a similar strategy in the ECDC assigned to the control arm. We will first calculate the number of families that were invited to participate in the program based on the number of children served by the center relative to the total number of children served by the 18 ECDC

in Tumaco. Then, we will distribute the ECDC across the 4 cohorts, ensuring that in each ECDC we assemble control groups at least once per year. Hence, larger ECDC in the control arm will have one or more control groups in each of the 4 cohorts, whereas the smaller ECDC will have at least one control group in 2018 and another one in 2019.

Then, we will randomly order eligible subjects within each center to be invited to participate in the different phases of data collection. Invitations will be carried out by the data collection team three weeks prior to the start of the intervention. Eligible subjects will be contacted at the ECDC or by phone and will be informed of the objectives and structure of the data collection and the potential benefits, including small incentives (super market cash cards for up to US\$8) for completing the data collection.

Eligible subjects will also be informed that their decision to participate in the data collection does not have any consequence on access to Genesis Foundation's programs in the municipality, including their children's access to the ECDC, or their participation in standard community groups and activities.

All randomization procedures will be conducted using the RANDOMIZE module (Kennedy & Mann, 2015), available in Stata 15. In doing so, we achieve balance on key characteristics at each phase of the randomization procedure.

- Randomization Unit

1st stage/level: Early Childhood Development Center. 2nd stage/level: individual - primary caregiver

- Was the treatment clustered?

Yes

- **Planned Number of Clusters**

- 18 (9 per treatment arm).

- **Planned Number of Observations.**

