- 40 groups of 16 participants in treatment and 640 participants in the control arm. (n = 1280)

- **Minimum detectable effect size for main outcomes (accounting for sample design and clustering)**

With 1280 participating households, nested in 18 child development centers, half of which are randomly assigned to an implementation cohort of the program, we estimate to have 80% of power to detect effect sizes ranging from 0.262 to 0.2221 at minimum. This range of minimal detectable effect sizes (MDES), is based on estimates in which we define a 0.05 probability of type I error, assign 9 clusters and half of the individual-level sample (640) to the treatment, and employing two-tailed tests in all our estimations. For all our estimations, we assume an Intra-class correlation coefficient (ICC) of 0.04, based on pilot estimations and a review of the literature. All power calculations were conducted with Power-Up! (Dong & Maynard, 2013), and validated using EGAP's Online Power Calculation Tool.

The smaller estimated MDES assumes that no covariates will be used in the estimation models, which would account for 30% of outcome variability explained by demographic covariates. Considering the range of effect sizes observed in the pilot evaluation, we consider that this study is adequately powered to detect smaller effects sizes than those previously reported. Assuming an attrition rate of 8%, the effective sample, we still be powered to detect effect sizes of 0.27. Telephonic check-ups and small incentives will be used to minimize attrition.

Note: Security conditions have worsened in Tumaco, leading to some uncertainty regarding our ability to implement the program in 2019. In this extreme case, the trial would only be run over the two 2018 cohorts, with 640 participating households, nested in 18 child development centers, half of which are randomly assigned to an implementation cohort of the program. In such case, we estimate to have 80% of power to detect effect sizes ranging from 0.341 to 0.405 at minimum. This range of minimal detectable effect sizes (MDES), is based on the same estimates as above: 0.05 probability of type I error, 9 clusters and half of the individual-level sample (320) assigned to the treatment, two-tailed statistical tests in our estimations and an Intra-class correlation coefficient (ICC) of 0.04. If we account for covariates, and assuming an attrition rate of 8%, we be powered to detect effect sizes of 0.404.

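### The full-trial minimum detectable effect (0.262 to 0.2221) lies below what its own inputs give (about 0.325 and 0.272) and has no term for the treated arm's therapy groups or facilitator dyads

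*Protocol*

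**What the plan says.** All references are to the protocol.

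- **Minimum detectable effect size, structure:** "With 1280 participating households, nested in 18 child development centers, half of which are randomly assigned to an implementation cohort of the program". The type I error and allocation are given as: "we define a 0.05 probability of type I error, assign 9 clusters and half of the individual-level sample (640) to the treatment". Tests are two-sided.
- **Same section, ICC:** "For all our estimations, we assume an Intra-class correlation coefficient (ICC) of 0.04, based on pilot estimations and a review of the literature". The level of this ICC is not named, but centres are the only clusters in the calculation.
- **Same section, result:** "we estimate to have 80% of power to detect effect sizes ranging from 0.262 to 0.2221 at minimum". Covariates are taken to explain 30% of outcome variability. The sentence that links covariates to the range attaches the smaller figure to the model without them, which is the wrong way round. Below, 0.262 is read as without covariates and 0.2221 as with them.
- **Same section, 2018-only note:** 640 households in the same 18 centres, same ICC, range 0.341 to 0.405.
- **Planned Number of Observations:** "40 groups of 16 participants in treatment and 640 participants in the control arm".
- **Intervention(s):** groups of 14 to 16 meet weekly for 15 sessions. Staffing: "The team of trained social workers will be assigned into three dyads". Each dyad leads 3 to 4 groups per cohort. The cohorts have 9, 9, 12 and 12 groups.
- **Experimental Design Details:** control groups are assembled for data collection. They receive no sessions.

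**The concern.** People treated together in a group by the same facilitators tend to have correlated outcomes because of the treatment itself. That adds variance to the treated-arm mean and none to the control mean. A calculation with one centre-level ICC common to both arms does not represent it, although the section heading suggests that clustering has been dealt with.

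The protocol concludes from these figures that the study is adequately powered. If the printed MDES is too small, the 80% power attached to it is overstated and a null result would be read as more informative than it is. So two things need checking: whether the printed range follows from its own inputs, and how much the missing level adds.

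**Working it through.** **Inputs from the protocol.** 9 centres per arm; 640 caregivers per arm (320 in the 2018-only case); ICC 0.04; two-sided 0.05; power 80%; R² = 0.30. **Assumed, not in the protocol:** group ICC ρg of 0.02 to 0.10; dyad ICC of 0.01; R² acting equally at centre and individual level. That last assumption favours the plan: if R² acts at the individual level only, the result is 2.985 × √[2 × (0.04/9 + 0.7 × 0.96/640)] = 0.313.

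**Step 1. The plan's own figure.**

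Variance of the difference = 2 × (0.04/9 + 0.96/640) = 0.01189, so SE = 0.1090.

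Multiplier with 18 − 2 = 16 df: 2.120 + 0.865 = 2.985 (normal approximation: 2.80).

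| | Printed | t, 16 df | Normal |
|---|---|---|---|
| No covariates | 0.262 | 2.985 × √0.01189 = 0.325 | 0.306 |
| R² = 0.30, both levels | 0.2221 | 2.985 × √(0.7 × 0.01189) = 0.272 | 0.256 |

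The printed range is not reproduced. Without covariates the recomputed value is higher by 0.325/0.262 = 1.24 (t) or 0.306/0.262 = 1.17 (normal). To obtain 0.262 without covariates, the ICC would have to be about 0.021 (t) or 0.026 (normal) instead of 0.04, or there would have to be about 28 to 32 clusters.

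The figure of 0.27 after 8% attrition does roughly agree with the formula: with 640 × 0.92 = 588.8 per arm and R² = 0.30, the result is 0.275.

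**Step 2. Are the two printed ranges compatible?** With 18 centres fixed, halving the sample can raise the MDES by at most √2 = 1.41, and at ICC 0.04 by 0.364/0.325 = 1.12. The printed upper figures have a ratio of 0.405/0.262 = 1.55. The two ranges cannot come from the same inputs, although the note says that they do.

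**Step 3. Add the therapy-group term, treated arm only.** Add ρg × (1/G − 1/640) with G = 40, that is, ρg × 0.02344.

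| ρg | No covariates | R² = 0.30, group term not reduced | R² = 0.30, group term also reduced |
|---|---|---|---|
| 0 | 0.325 | 0.272 | 0.272 |
| 0.02 | 0.332 (+2%) | 0.280 (+3%) | 0.278 |
| 0.05 | 0.341 (+5%) | 0.291 (+7%) | 0.285 |
| 0.10 | 0.356 (+9%) | 0.308 (+13%) | 0.298 |

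The effect is modest because groups are nested in randomised centres: 0.04/9 = 0.0044 per arm outweighs, for example, 0.05/40 = 0.00125. The cohort counts give 9 + 9 + 12 + 12 = 42 groups, not 40. With G = 42 the result at ρg = 0.05 is 0.340, so this discrepancy hardly affects the size.

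**Step 4. Dyads.** If the three dyads are treated as a random sample, a dyad ICC of 0.01 adds 0.01/3 to the variance. On the centre-only calculation the MDES goes from 0.325 to 2.985 × √(0.01189 + 0.00333) = 0.368 (+13%). If inference is conditional on these three dyads, the addition is zero.

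**Step 5. The 2018-only case.** Centre-only: 2.985 × √[2 × (0.04/9 + 0.96/320)] = 0.364, and 0.305 with R² = 0.30. The printed 0.405 and 0.341 are larger. With 18 groups, ρg = 0.02, 0.05 and 0.10 gives 0.377, 0.395 and 0.423 without covariates. The printed figures are exceeded only when ρg is above roughly 0.05 to 0.08, depending on how covariates are handled and on whether 18 or 320/16 = 20 groups are used, or if there is a dyad effect.

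**The case against.** The strongest reply is that the omission is small and its size is not known. The protocol gives no group or dyad ICC. Its 0.04 rests partly on a pilot of this group programme, so it may already contain some between-group variance. The section heading reads like a registry form prompt, and centre clustering, the level of randomisation, is in the inputs. All of this is fair, and it limits the group term to a sensitivity analysis. It does not remove the point. If the 0.04 does hold treatment-group variance, it is wrong for the control arm. And the failure in Step 1 needs no group ICC at all.

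A reader might draw four stronger conclusions that the documents do not support:

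- *That the printed MDES is too small because groups were left out.* Most of the shortfall is there before any group term is added.
- *That the 2018-only range is also too small.* It exceeds what the centre-only inputs give, and remains above it for small group ICCs.
- *That shared dyads make the treated centres dependent by a known amount.* The protocol does not say how dyads map to centres, and the 13% holds only if three dyads are regarded as random.
- *That the protocol should specify a partially nested analysis model.* That commonly belongs in the statistical analysis plan, which is not at hand.

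**Conclusion.** The point holds for the full-trial range. Printed as 0.262 to 0.2221, it should read about 0.325 without covariates and 0.272 with them on the stated inputs (t, 16 df; R² of 0.30 at both levels). Even the normal approximation gives 0.306 and 0.256. A treated-arm group term at an assumed ICC of 0.02 to 0.10 takes these to about 0.33 to 0.36 and 0.28 to 0.31 (0.30 at the top if covariates also reduce the group term). The two problems act in the same direction.

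That no input covers the groups and dyads is a fact of the document. How much they add depends wholly on assumed ICCs and, for dyads, on a choice about inference. For the 2018-only range the finding is inconsistency with the full-trial range, not understatement. The correction should be made, because the statement of adequate power rests on these figures; trial conduct is unaffected.

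**What to change.** 1. Restate the full-trial MDES from the stated inputs, giving the level of the ICC, the degrees of freedom, and the level at which R² = 0.30 applies. Correct the sentence that assigns the smaller value to the model without covariates.
2. Add sensitivity rows with ρg × (1/G − 1/640) in the treated-arm variance for group ICC 0.02, 0.05 and 0.10, labelled as assumptions. Say whether the 0.04 is thought to include any group variance.
3. Reconcile 40 groups with the cohort counts that add to 42, and use the agreed number as G.
4. State that inference is conditional on the three dyads, or add a dyad row labelled as an assumption.
5. Recompute the 2018-only range on the same basis, so that both ranges share inputs.

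The cost is one recalculation and some wording. The dyads already complete session logs on participants, so group and dyad membership should be recordable. The downside is a less favourable stated full-trial MDES.

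### The protocol ties the smaller MDES (0.2221) to a model without covariates, which is backwards, and swapping the labels would not make the figures fit the stated inputs

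*Protocol*

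**What the plan says.** All of this stands in the protocol section on the minimum detectable effect size for main outcomes, including its closing Note.

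- Full trial: "we estimate to have 80% of power to detect effect sizes ranging from 0.262 to 0.2221 at minimum". The inputs are given there: "With 1280 participating households, nested in 18 child development centers", and "we define a 0.05 probability of type I error, assign 9 clusters and half of the individual-level sample (640) to the treatment", "employing two-tailed tests in all our estimations", with an ICC of 0.04 throughout.
- Which model gives which figure: "The smaller estimated MDES assumes that no covariates will be used in the estimation models, which would account for 30% of outcome variability", the variability being that explained by demographic covariates. This is the only sentence that links either end of the range to a model.
- With 8% attrition, no model named: "we still be powered to detect effect sizes of 0.27".
- Note, for a trial confined to the two 2018 cohorts (640 households, same 18 centres, same ICC): a range of 0.341 to 0.405, and then 0.404 under the condition "If we account for covariates, and assuming an attrition rate of 8"%.

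**The concern.** Adjusting for covariates that explain 30% of the outcome variance removes residual variance, so the adjusted model has the smaller MDES. The sentence gives the smaller value to the model without covariates. It also contradicts itself, because covariates that are left out cannot account for 30% of anything.

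Taken as written, the protocol credits an unadjusted analysis with 80% power at 0.2221. The section goes on to call the study adequately powered, and a reader cannot tell which model that conclusion rests on. The attrition figures do not help: one has no model label, and the other is said to include covariates yet sits almost at the unfavourable end of its range.

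**Working it through.** **Inputs.** J = 18 centres, half to each arm (P = 0.5); N = 1280; ICC = 0.04; two-sided alpha 0.05; power 80%; R² = 0.30; attrition 8%. All are from the power section. The protocol does not say at which level the 30% applies, so caregiver level only and both levels are shown.

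**Formula** (two-level cluster-randomised design):

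MDES = M × sqrt[ ICC(1 − R²_centre)/(P(1 − P)J) + (1 − ICC)(1 − R²_caregiver)/(P(1 − P)N) ]

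M = t(0.975; 16) + t(0.80; 16) = 2.985, or 2.802 by the normal approximation.

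**Step 1: direction, from the protocol's own figures.** 0.2221/0.262 = 0.848 and, in the Note, 0.341/0.405 = 0.842. Explaining 30% of the variance at both levels multiplies the MDES by sqrt(0.70) = 0.837. Both pairs look like an unadjusted value and an adjusted one, with the smaller adjusted.

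**Step 2: attempt to reproduce the range.** Without covariates, N = 1280:

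- centre term: 0.04 × 4/18 = 0.00889
- caregiver term: 0.96 × 4/1280 = 0.00300
- standard error: sqrt(0.01189) = 0.1090
- MDES: 2.985 × 0.1090 = 0.325 (normal: 0.305)

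The same steps elsewhere give (t / normal):

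| | No covariates | R² = 0.30, caregiver level only | R² = 0.30, both levels |
|---|---|---|---|
| N = 1280 | 0.325 / 0.305 | 0.313 / 0.294 | 0.272 / 0.256 |
| N = 1178 (8% loss) | 0.329 / 0.309 | 0.315 / 0.296 | 0.275 / 0.258 |
| N = 640 | 0.364 / 0.342 | 0.341 / 0.321 | 0.305 / 0.286 |
| N = 589 (8% loss) | 0.371 / 0.348 | 0.346 / 0.325 | 0.310 / 0.291 |

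The pair 0.262 and 0.2221 is not reproduced. The adjusted value is smaller in every row. Lost degrees of freedom do not plausibly reverse this: with R² = 0.30 at both levels, about 12 centre-level covariates among 18 centres would be needed before the adjusted MDES exceeded 0.325.

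**Step 3: power at 0.2221, N = 1280** (noncentral t / normal).

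- No covariates: 48% / 53%.
- R² = 0.30, caregiver level only: 51% / 56%.
- R² = 0.30, both levels: 63% / 68%.

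To reach 80% at 0.2221, R² at both levels would have to be about 0.53 (t) or 0.47 (normal).

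**Step 4: would 0.262 serve as the no-covariate value?** Only with an ICC of about 0.021 (t) to 0.026 (normal). The Note's 0.405, read the same way, needs about 0.056 to 0.068. The protocol states 0.04 for both. On the stated inputs 0.262 lies among the both-level adjusted values (0.256 to 0.272).

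**Step 5: attrition.** With the 18 centres fixed, losing 8% of caregivers inflates only the caregiver term. The no-covariate MDES goes from 0.325 to 0.329, a factor of 1.011. Applied to the stated ends of the range this gives 0.262 × 1.011 = 0.265 and 0.2221 × 1.011 = 0.225, neither of which is 0.27. In the Note, moving from 0.341 to 0.404 would be a rise of 18% (0.404/0.341 = 1.185), where the formula gives under 2% (0.371/0.364). If 0.341 is the adjusted value, 0.404 cannot be its counterpart with 8% attrition.

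**The case against.** The strongest reply is that this is a drafting slip. The sentence itself mentions 30% explained by demographic covariates, so a statistician would see what was meant, and no analysis depends on it. That it is a slip is likely. It is still the only statement of which model delivers which power, nothing elsewhere in the protocol corrects it, and the figures around it do not allow a safe guess.

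Three stronger readings are tempting, and the protocol does not support them.

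- *A simple swap.* A reader might infer that 0.262 is the right unadjusted figure and 0.2221 the right adjusted one. The ratio shows only which was probably meant as adjusted, and it fits R² at both levels, which the protocol does not state; at caregiver level only the ratio would be 0.313/0.325, about 0.96. Neither figure follows from the stated inputs.
- *That 0.27 belongs to the model without covariates.* Since 0.262/sqrt(0.92) = 0.273, this looks neat, and the same step would turn 0.2221 into 0.232. That scaling is for independent observations, not for 18 fixed centres. With the cluster formula, 0.27 falls among the both-level adjusted values at N = 1178 (0.258 to 0.275) and outside the unadjusted ones (0.309 to 0.329). The model behind 0.27 cannot be settled from the text, and 0.232 should not be used.
- *That the trial would drop its covariates.* The section describes a power assumption and does not prescribe an analysis model; that may stand in a SAP that is not at hand. The harm is a misattributed power claim.

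**Conclusion.** The point holds as a misstatement in the protocol. The smaller MDES cannot belong to the model without covariates; on the stated inputs that model has about 48% power at 0.2221 (53% by the normal approximation) and an MDES of about 0.325 (0.305). Relabelling alone leaves 0.2221 unsupported, because the adjusted model at R² = 0.30 has an MDES of about 0.272 (both levels) or 0.313 (caregiver level only).

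The direction of the error needs no assumption beyond the 30% and a sensible number of covariates. The sizes assume equal centre sizes (about 71 caregivers each), the stated ICC of 0.04, centres as the only level of clustering, and one of the two placements of R². The attrition labels are unresolved: 0.27 has no model, and 0.404 is said to include covariates yet all but equals the top of the Note's range (0.405). The finding concerns how power is stated, not how the trial is run.

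**What to change.** 1. Reverse the sentence so that the smaller MDES belongs to the covariate-adjusted model and the larger to the model without covariates.
2. State whether R² = 0.30 is assumed at caregiver level, centre level or both, and how many centre-level covariates are allowed for.
3. Recompute and restate the MDES for both models, for the full trial and for the 2018-only scenario. If the inputs stand, the full-trial values are about 0.325 without covariates and 0.272 or 0.313 with them. If other inputs were used, state them.
4. Label each 8% attrition figure with its model, recompute it with the cluster formula, and reconcile 0.404 with the range of 0.341 to 0.405.
5. Say which model the statement of adequate power rests on.

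The cost is one recalculation and a few sentences. The stated sensitivity of the full trial becomes less favourable. Nothing in the conduct of the trial changes.
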